8.4 Withdrawal of individual subjects

Subjects can leave the study at any time for any reason if they wish to do so without any penalty or loss of medical benefits. Subjects can also be withdrawn from the study procedures at the discretion of the clinical investigator or the local safety monitor for urgent medical reasons or if exclusion criteria are met. The following reasons may lead to withdrawal of individual subjects:

- Withdrawal of informed consent by volunteer;
- Any serious adverse event;
- Any adverse event that, according to clinical judgment of the investigator, is considered as a definite contraindication to proceeding with the study procedures;
- Immunosuppressant or other immune-modifying drugs administered chronically (i.e., more than 14 days in total) during the study period. Topical steroids are allowed;
- Immunoglobulin and/or any blood products administered during the study period;
- Pregnancy;
- Completely lost to follow-up;
- Ineligibility (arising during the study or retrospectively, having been overlooked at screening);
- If the investigator or safety monitor believes that continuation would be detrimental to the subject's well-being;
- Volunteer non-compliance with study requirements;
- Any other protocol deviation that results in a significant risk to the subject's safety.

For subjects lost to follow-up (i.e. those subjects whose status is unclear because they fail to appear for study visits without stating an intention to withdraw), extensive effort (i.e. documented phone calls and e-mails) will be undertaken to locate or recall the volunteer or at least to determine his or her health status. The investigator should show "due diligence" by documenting in the source documents steps taken to contact the subject. In case of premature withdrawal for any reason, the investigator will exert his/her best effort to:

- Update any ongoing AE/SAEs that remained ongoing at the time of the subject's last visit prior to withdrawal.
- Determine if the subject has had any reaction or AE since the last visit. Where possible, the investigator should visibly or physically assess any reported adverse reaction or AE and document whether it led to the withdrawal.
- Collect blood for biochemical and hematological clinical laboratory parameters.
- Review the subject's memory aid if it is still in use at the time of withdrawal.
- Document the reason for premature withdrawal on the CRF.

8.5 Replacement of individual subjects after withdrawal

If an assigned subject does not present on the day of first R0.6C administration or elects to withdraw the consent on the day of administration, one of the reserve subjects will replace the subject. After subjects have received R0.6C administration they cannot be replaced.

8.6 Follow-up of subjects withdrawn from treatment

A subject may end his or her participation in the study and still be followed up for safety, unless the subject chooses to have complete withdrawal of the consent for further participation in any trial procedures. If a subject chooses to withdraw from the study, the investigator will make a reasonable effort to determine the reason for the subject's withdrawal and complete the study termination eCRF.

8.7 Premature termination of the study

The study may be discontinued by the sponsor:

- On advice of the safety monitor
- On advice of the Safety Monitoring Committee (SMC)
- On advice of the clinical investigator
- On advice of the METC

The investigators, local safety monitor, SMC, METC or Sponsor may decide to put the study on hold based on adverse events, pending discussion with the Sponsor, SMC, METC, local safety monitor or investigators. Following discussion, it may be decided to terminate the study.

9. SAFETY REPORTING

9.1 Temporary halt for reasons of subject safety

In accordance to section 10, subsection 4, of the WMO, the sponsor will suspend the study if there is sufficient ground that continuation of the study will jeopardise subject health or safety. The sponsor will notify the accredited METC without undue delay of a temporary halt including the reason for such an action. The study will be suspended pending a further positive decision by the accredited METC. The investigator will take care that all subjects are kept informed.

9.2 AEs, SAEs and SUSARs

9.2.1 Adverse events (AEs)

Adverse events are defined as any undesirable experience occurring to a subject during the study, whether or not considered related to the investigational product. All adverse events reported spontaneously by the subject or observed by the investigator or his staff will be recorded. Abnormal laboratory findings (e.g. clinical chemistry or hematology) or other abnormal assessments that are judged by the investigator to be clinically significant will be recorded as AEs (or SAEs if they meet the definition). The investigator will exercise his or her medical and scientific judgment in deciding whether an abnormal laboratory finding or any other abnormal assessment is clinically significant. If there are any severe complaints, the volunteer will be evaluated immediately by a qualified clinician using the appropriate clinical assessments according to standard hospital care.

9.2.2 Adverse event data collection and recording

Adverse events will be collected at all follow-up visits, using the memory aid booklets as a basis (see section 8.3.9), and whenever a subject reports signs or symptoms to the trial physician between visits.

After administration with R0.6C the following systemic signs and symptoms will be solicited until 14 days after administration:

Fever, headache, myalgia, fatigue, chills, and rash. The time points that these symptoms are solicited are indicated in section 8.3.17.

After the administration of R0.6C the following local signs and symptoms will be solicited until 7 days after administration:

Pain, itching, swelling, induration and redness at injection site. The time points that these symptoms are solicited are indicated in section 8.3.17.

If known, the trial clinician will record the diagnosis (i.e., disease or syndrome) rather than component signs, symptoms and laboratory values. If the signs and symptoms are considered unrelated to an encountered syndrome or disease they should be recorded as individual AEs. If a primary AE is recorded, events occurring secondary to the primary event should be described in the narrative description of the case (e.g. primary AE = Orthostatic hypotension; secondary event may be fainting, head trauma, etc.). In case of hospitalizations for surgical or diagnostic procedures, the pre-existing condition should be recorded as the SAE, not the procedure itself.

All adverse events/reactions (solicited and unsolicited) will be accurately documented in the case report form by the investigators. For each event/reaction the following details will be recorded:

1. Description of the event/reactions (ICD-10 terminology will be included in the eCRF)
2. Duration (date and time of occurrence and end date and time)
3. Intensity (see explanation directly below)
4. Relationship with the intervention (see section 9.2.3)
5. Action taken, including treatment

The intensity of the symptoms will be ranked as (1) mild, (2) moderate, (3) or severe, according to the following scale:

Mild (grade 1):	awareness of symptoms that are easily tolerated and do not interfere with usual daily activity
Moderate (grade 2):	discomfort that interferes with or limits usual daily activity
Severe (grade 3):	disabling, with subsequent inability to perform usual daily activity, resulting in absence or required bed rest

If an adverse event changes in intensity during the specified reporting period, a new description of the adverse event will be added. Interrupted AEs are registered as one AE if the interruption is <24 hours. When an AE/SAE occurs, it is the responsibility of the investigators to review all documentation (e.g. hospital progress notes, laboratory, and diagnostics reports) related to the event. The investigators will then record all relevant information regarding an AE/SAE on the CRF or SAE Report Form, respectively.

9.2.3 Assessment of causality

The investigators are obliged to assess the relationship between study procedures and the occurrence of each AE/SAE. The investigators will use clinical judgment to determine the relationship. Alternative causes, such as natural history or the underlying diseases, concomitant therapy, other risk factors and the temporal relationship of the event will be considered and investigated. The relationship of the adverse event with the study procedures will be categorized as:

Definitely: administration of the IP is the cause, another etiology causing the adverse event is not known.

Probable: administration of the IP is the most likely cause: however, there are alternative reasonable explanations, even though less likely.

Possible: there is a potential association between the event and administration of the IP, however, there is an alternative etiology that is more likely.

Unlikely: a relationship to the administration of IP is unlikely, however, it cannot be ruled out.

Not related: a relationship to the administration of the IP cannot be reasonably established; another etiology is known to have caused the adverse event or is highly likely to have caused it.

When a regulatory authority requests a binary classification (related vs. unrelated), definitely, probably and possibly related are considered to be “related”, while not related and unlikely related are considered to be “unrelated”. Thus, an intervention-related AE refers to an AE for which there is a possible, probable or definite relationship to the study intervention. The investigator will use clinical judgment to determine the relationship.

9.2.4 Serious adverse events (SAEs)

A serious adverse event is any untoward medical occurrence or effect that:

- results in death;
- is life threatening (at the time of the event);
- requires hospitalisation or prolongation of existing inpatients' hospitalisation;
- results in persistent or significant disability or incapacity;
- is a congenital anomaly or birth defect; or
- any other important medical event that did not result in any of the outcomes listed above due to medical or surgical intervention but could have been based upon appropriate judgement by the investigator.

An elective hospital admission will not be considered as a serious adverse event. The investigator will report all SAEs to the sponsor without undue delay after obtaining knowledge of the events (within 24 hours). The sponsor will report all SAEs through the web portal *ToetsingOnline* to the accredited METC that approved the protocol, within 7 days of first knowledge for SAEs that result in death or are life threatening followed by a period of maximum of 8 days to complete the initial preliminary report. All other SAEs will be reported within a period of maximum 15 days after the sponsor has first knowledge of the serious adverse events.

9.2.5 Suspected unexpected serious adverse reactions (SUSARs)

Adverse reactions are all untoward and unintended responses to an investigational product related to any dose administered. Unexpected adverse reactions are SUSARs if the following three conditions are met:

1. the event must be serious (see section 9.2.4);
2. there must be a certain degree of probability that the event is a harmful and an undesirable reaction to the medicinal product under investigation, regardless of the administered dose;
3. the adverse reaction must be unexpected, that is to say, the nature and severity of the adverse reaction are not in agreement with the product information as recorded in:
 - Summary of Product Characteristics (SPC) for an authorised medicinal product;
 - Investigator's Brochure for an unauthorised medicinal product.

The sponsor will report expedited the following SUSARs through the web portal *ToetsingOnline* to the METC:

- SUSARs that have arisen in the clinical trial that was assessed by the METC;
- SUSARs that have arisen in other clinical trials of the same sponsor and with the same medicinal product, and that could have consequences for the safety of the subjects involved in the clinical trial that was assessed by the METC.

The remaining SUSARs are recorded in an overview list (line-listing) that will be submitted once every half year to the METC. This line-listing provides an overview of all SUSARs from the study medicine, accompanied by a brief report highlighting the main points of concern. The expedited reporting of SUSARs through the web portal Eudravigilance or *ToetsingOnline* is sufficient as notification to the competent authority. The sponsor will report expedited all SUSARs to the competent authorities in other Member States, according to the requirements of the Member States. The expedited reporting will occur not later than 15 days after the sponsor has first knowledge of the adverse reactions. For fatal or life threatening cases the term will be maximal 7 days for a preliminary report with another 8 days for completion of the report. As this is an open label study in which the sponsor, investigator and the SMC are not blinded, the code would not have to be broken in the case of a SUSAR.

9.3 Annual safety report

In addition to the expedited reporting of SUSARs, the sponsor will submit, once a year throughout the clinical trial, a safety report to the accredited METC, competent authority, and competent authorities of the concerned Member States.

This safety report consists of:

- a list of all suspected (unexpected or expected) serious adverse reactions, along with an aggregated summary table of all reported serious adverse reactions, ordered by organ system, per study;
- a report concerning the safety of the subjects, consisting of a complete safety analysis and an evaluation of the balance between the efficacy and the harmfulness of the medicine under investigation.

9.4 Follow-up of adverse events

All AEs will be followed until they have abated, or until a stable situation has been reached. Depending on the event, follow up may require additional tests or medical procedures as indicated, and/or referral to the general physician or a medical specialist.

SAEs need to be reported till end of study within the Netherlands, as defined in the protocol. After termination of the trial, the investigator should assure that the subject is referred for medical follow-up, as appropriate.

9.5 Safety Monitoring Committee

An independent SMC composed of three independent individuals will be appointed. The SMC will include a local safety monitor, and two experts nominated by the PI. The SMC will be established for the purpose of monitoring the study and to provide independent, non-binding advice on safety and ethics. The responsibilities and procedures of the SMC members are defined in the SMC Charter.

The advice(s) of the SMC will only be sent to the sponsor of the study. Should the sponsor decide not to fully implement the advice of the DSMB, the sponsor will send the advice to the reviewing METC, including a note to substantiate why (part of) the advice of the SMC will not be followed.

9.5.1 Local safety monitor

For this study, a local safety monitor will be appointed, who will be involved in the review of severe and serious adverse events and volunteer safety. He/she is independent of the sponsor and the investigator. The local safety monitor is notified of all grade 3 adverse events probably or definitely related to R0.6C administration and persisting at grade 3 for >48 hours.

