8. METHODS

8.1 Study endpoints

Primary safety Endpoints:

- 1) The number of serious adverse events and solicited and unsolicited grade 3 adverse events possibly, probably or definitely related to the vaccine in the period from first R0.6C administration up to 84 days after the last immunization.

Primary efficacy endpoints:

- 1) The functional transmission reducing activity in the standard membrane feeding assay of volunteer sera collected two weeks after the fourth R0.6C immunization (I4+14), compared to baseline (I1-1) within each of the four dose-adjuvant groups.

Secondary safety endpoints:

- 1) The number of solicited and unsolicited grade 1 and 2 adverse events possibly, probably or definitely related to the vaccine in the period from first R0.6C administration up to 84 days after the last immunization.

Secondary efficacy endpoints:

- 1) The TRA at other timepoints (I1+14, I2+14, I3+14, I3+111 [I4-1], and I4+84) compared to baseline (I1-1) in each of the four dose-adjuvant groups.
- 2) The anti-6C antibody quantity in volunteer sera collected two weeks after fourth R0.6C immunization (I4+14) and at other time points (I1+14, I2+14, I3+14, I3+111 [I4-1], and I4+84) compared to baseline (I1-1) in each of the four dose-adjuvant combinations, as determined by ELISA.

Exploratory Endpoints:

- 1) The functional TBA in the SMFA of volunteer sera collected at different time points compared to baseline (I1-1) in each of the four dose-adjuvant combinations.
- 2) The anti-6C antibody decay rate following R0.6C immunization for each of the four dose-adjuvant combinations.
- 3) The anti R0.6C and anti-R0 antibody quantity in volunteer sera collected at different time points in each of the four dose-adjuvant combinations.
- 4) The cellular immune responses in volunteers samples collected at different time points in each of the four dose-adjuvant combinations.
- 5) The difference in TRA between the two dose groups (30 or 100 μ g R0.6C) and/or between adjuvant groups (alhydrogel and alhydrogel+Matrix-M).
- 6) The difference in peak anti-6C antibody quantity between the two dose groups (30 or 100 μ g R0.6C) and/or between adjuvant groups (alhydrogel and alhydrogel+Matrix-M).

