9.5.5 Safety holding rules

The study may be placed on safety hold at any time for the following reasons:

- On advice of the safety monitor;
- On advice of the Principal/Clinical investigators;
- On advice of the SMC;
- On advice of the CCMO;
- If holding rules are met (see below).

If the following holding rules are met, administration of R0.6C will be held for all remaining administrations in that dosage group and subsequent groups:

- One or more participants experience a SAE that is determined to be at least possibly related to the administration of R0.6C
- Two or more subjects experience a grade 3 adverse event (local, clinical systemic or laboratory systemic) possibly, probably or definitely related to R0.6C administration and persisting at grade 3 for >72 hours

If considered necessary by the investigators or SMC, remaining administrations in lower dosage groups may also be put on hold.

The study site member first aware of the event meeting the holding rule will notify the Principal Investigator and the Local Safety Monitor. The PI will alert the appropriate parties. The SMC will be notified within 24 hours. An ad hoc SMC review will be performed. The following considerations must be discussed:

- Relationship of the AE or SAE to the study product
- Relationship of the AE or SAE to R0.6C dose
- Relationship of the AE or SAE to (one of) the adjuvants
- If appropriate, additional screening or laboratory testing is provided to other subjects to identify subjects who may develop similar symptoms
- If any study related SAE is not listed on the current informed consent form (ICF), the PI will revise the ICF and subjects will be asked to provide consent on the new ICF

R0.6C administration to subjects within the affected group and to the next (higher dosage) group may resume only if the local safety monitor, PI, SMC and the sponsor agree it is safe

to resume R0.6C administration. It may be decided to proceed with only R0.6C adjuvated with Alhydrogel (groups A) or only R0.6C adjuvated with Alhydrogel and Matrix-M (groups B). If the CCMO has recommended safety hold, re-initiation of the study will require CCMO concurrence. The CCMO will be informed of a safety hold by the sponsor. Following discussion, it may be decided to terminate the study.

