10.2 Interim analysis

There are no statistical criteria for study termination in this clinical trial. Safety and reactogenicity data will be evaluated after each R0.6C administration before proceeding to the next group. A summary report of AEs will be provided to the SMC after all four groups have completed follow-up.

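### Protocol 9.5.1 sets no duty to alert the local safety monitor individually to a first subject's possibly related grade 3 event, although that event counts towards the hold in 9.5.5

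*Protocol*

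**What the plan says.** **The alert.** Protocol 9.5.1 has the local safety monitor, who is independent of sponsor and investigator, notified of "grade 3 adverse events probably or definitely related to R0.6C administration and persisting at grade 3 for >48 hours". The same section says more generally that the monitor "will be involved in the review of severe and serious adverse events and volunteer safety".

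**The hold.** Under Protocol 9.5.5, dosing is held once two or more subjects have a grade 3 event that is "possibly, probably or definitely related to R0.6C administration and persisting at grade 3 for >72 hours". A single SAE that is at least possibly related also triggers a hold. The SAP section on interim analyses and stopping guidance repeats both rules. When an event meets a holding rule, the site must tell the principal investigator and the monitor, and the SMC must hear within 24 hours.

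**Causality.** Protocol 9.2.3 puts the grading with the site: "The investigators will use clinical judgment to determine the relationship". A possible relationship means that "there is a potential association between the event and administration of the IP, however, there is an alternative etiology that is more likely". The section nevertheless places possible on the related side when a yes/no classification is needed.

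**Scheduled review.** The monitor sits on the SMC (Protocol 9.5). Under 9.5.2 and 8.3.17 footnote 9, the SMC reviews data before each next group starts and again after all follow-up. Protocol 10.2 says data are "evaluated after each R0.6C administration before proceeding to the next group"; the SAP ties this review to the first administration in each group.

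**The concern.** Possibly related grade 3 events count fully towards the hold but are absent from the alert. For probably or definitely related events, the 48-hour alert is triggered a day before the 72-hour holding threshold. Possibly related events have no such step.

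What is at stake is early independent notice. The data are recorded either way. The investigators assign the causality grade, so their choice between possible and probable decides whether the independent monitor must be told of a first subject's event.

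That notice has a use below the two-subject threshold. Protocol 8.4 lists as a ground for withdrawing one subject: "If the investigator or safety monitor believes that continuation would be detrimental". Under 9.5.5 the monitor may also advise a hold at any time, or stop or suspend use of the product. A monitor who has not been told cannot weigh any of these steps, in a first-in-human trial where each subject is due four doses.

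**Working it through.** The plan states no figure for this point. The check compares the rules and then counts doses.

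**1. Which rule obliges someone to tell the monitor?** Take grade 3 events lasting more than 72 hours, plus the SAE case.

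| Event | Alert under 9.5.1 | Counts towards hold (9.5.5) | Notice because a holding rule is met |
|---|---|---|---|
| First subject, non-serious, probably or definitely related | Yes, past 48 h | Yes | No, one subject only |
| First subject, non-serious, possibly related | Not required | Yes | No, one subject only |
| Second subject, non-serious, possibly related | Not required | Yes | Yes, past 72 h |
| Any subject, SAE at least possibly related | Not needed | Yes, alone | Yes, at once |

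The second row is the gap. There is also a mixed case. If the first subject's event is possibly related and the second's probably related, the monitor gets a 48-hour alert for the second without necessarily knowing that one more day at grade 3 would trigger a hold.

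**2. How much can go without individual notice?** Protocol 9.5.5 counts subjects, and one subject could have several qualifying events over four doses. It does not say whether the two subjects are counted across the trial or within a dosage group. The number who can qualify before a notice is due is therefore 1 if counted across the trial, up to 2 if counted per dose level (30 and 100 µg), or up to 4 if counted per group 1 to 4.

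**3. How much dosing follows the last inter-group review?** Inputs from Protocol sections 4 and 6.1:
- Group sizes are 6, 10, 6 and 10, which sum to 32.
- Doses fall on days 0, 28, 56 and 168, so 32 × 4 = 128 planned doses.
- Groups start at least 14 days apart.

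Assume every group starts at the minimum spacing, that is on days 0, 14, 28 and 42, with all its subjects dosed on the first day. Doses given before day 42:
- Group 1, days 0 and 28: 6 × 2 = 12
- Group 2, day 14 (its second dose falls on day 42 itself): 10 × 1 = 10
- Group 3, day 28: 6 × 1 = 6

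The sum is 12 + 10 + 6 = 28, so 128 − 28 = 100 doses fall on or after the start of group 4. If earlier groups finished all dosing first, group 4's own 10 × 4 = 40 would remain. The range is thus 40 to 100 of 128, or 31% to 78%.

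**4. How long is the scheduled wait?** The final report follows the last group 4 visit, which Protocol 8.3.17 places on day 252 after that subject's first dose. With no second qualifying subject and no extra review, an event soon after group 4 starts could wait about 252 days for a scheduled report.

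**5. Do Protocol 10.2 and the SAP differ in effect?** One refers to each administration and the other to the first. Both tie the review to moving to the next group, and group 4 has no next group.

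**The case against.** The strongest reply is that an alert and a hold are different tools. An alert that comes earlier but demands stronger attribution is coherent, because a possible relationship means another cause is more likely. No text says the alert must cover everything that counts towards a hold. Section 9.5.1 does not exclude other notices and gives the monitor a general part in reviewing severe events, without a relatedness limit. SMC reports list adverse events by severity, review frequency may be adapted, and ad hoc meetings can be called. The SMC Charter sets members' procedures and has not been seen.

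Much of this stands, and it makes the gap modest. It does not close the gap. The general role carries no duty to notify and no timing, extra reviews are optional, and the documents do not give the definition of possible as the reason for the narrower alert. The Charter may settle the matter, but that cannot be checked here.

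A reader might infer that the primary safety endpoint is affected, since Protocol 8.1 counts "solicited and unsolicited grade 3 adverse events possibly, probably or definitely related to the vaccine". It is not. That count has no duration limit and does not depend on who is notified.

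**Conclusion.** The mismatch is in the current text, and no provided section requires individual notice of a first subject's non-serious, possibly related grade 3 event. It is worth a cheap correction and no more.

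Three stronger readings are tempting, and the documents do not support them:
- **The holding rule fails.** It does not. Investigators record and grade every event, a second qualifying subject triggers both the hold and notice to the monitor, and a possibly related SAE triggers them at once.
- **Only group 4's 10 subjects are exposed.** Later doses in the earlier groups can also fall after the last inter-group review.
- **At most one event can go unnotified.** The rule counts subjects, so one subject may contribute several events.

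The 100-dose figure rests on minimum spacing and same-day dosing within groups; the 40-dose floor does not. Both measure dosing without a scheduled inter-group review. Neither is an expected number of missed alerts, because the documents give no rate for these events.

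**What to change.** In Protocol 9.5.1, extend the alert to grade 3 events that are possibly, probably or definitely related, and keep the duration at more than 48 hours. Wider scope alone does not secure early notice, because 9.5.1 sets no deadline. Add that notice is given promptly once 48 hours is passed, for example within 24 hours. Since 48 + 24 = 72, such notice can reach the monitor by the holding threshold. Align the SMC Charter; if it already requires this, the change only makes the two documents agree.

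The cost is a small amended text and a few more notifications. If 1%, 5% or 10% of subjects had such an event (assumed rates, not from the documents) and each led to one notice, 32 × 0.01 = 0.3, 32 × 0.05 = 1.6 and 32 × 0.10 = 3.2 extra notices would be expected over the trial. A subject with repeated events would add more. Holding thresholds, endpoints and analyses stay as they are.
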